At baseline, twelve participants (six from each arm of the study) will be invited to participate in **six semi-structured individual interviews**, which will take place at the same time as the quantitative data collection: **baseline, month six, month 12, month 18, month 24, and month 30**. Participants will be purposively selected with a goal of having input from each of the three communities and a fairly equal gender and ethno-racial representation.

All of the mentors ($n = 12$) will be invited to participate in **two focus groups**, which will take place at **month 12 and month 24**.

The questions posed during the semi-structured interviews and focus groups will be guided by the study objectives, but will be conversational and exploratory in nature with particular attention to understanding *how* mentoring and/or rent subsidies influence social integration outcomes for formerly homeless young people living in market rent housing. Given the emergent nature of qualitative inquiry (Denzin & Lincoln, 2011; Eakin & Mykhalovskiy, 2003), we expect the interview and focus group questions to evolve over time as key preliminary themes begin to surface. It is anticipated that the individual interviews (including quantitative data collection, which will consistently take place first) will last approximately 60 – 75 minutes, and the focus

groups approximately 60 – 90 minutes. The individual interviews and the focus groups will be conducted by [name] at locations most convenient for those participating. To get a better sense of each young person’s living situation and to minimize researcher – participant power imbalance (Israel et al., 2018), [name] will suggest that the individual interviews take place in or nearby the young people’s homes. The individual interviews and focus groups will be audio recorded and transcribed verbatim.

4e. Honoraria

All of the study participants will be paid an honorarium of \$20 at each of the six quantitative data collection points. Those participating in semi-structured interviews will be paid an additional \$30 at each interview. This amount was based on the co-investigator’s previous experience with this population and after consulting with our community partners.

5. Data Analysis

One major critique of mixed methods RCTs is that, typically, there is no true integration (i.e., ‘mixing’) of quantitative and qualitative findings at the level of analysis or interpretation (Lewin, Glenton, & Oxman, 2009). Moreover, it is often unclear whether or how the quantitative and qualitative researchers have worked together to maximize the potential synergies between these different approaches (Lewin et al.). With this in mind, our study team, consisting of researchers with quantitative and qualitative expertise, worked together to develop this study protocol and anticipate meeting quarterly to discuss the emerging analysis and to explore (and follow up on) similarities or discrepancies between the quantitative and qualitative data.

5a. Quantitative Data

All analyses will be performed using the intention-to-treat principle; that is, all participants will be included and analyzed in the groups they were originally randomized. Baseline characteristics of the intervention and control groups will be summarized using descriptive statistics (i.e., mean, standard deviation, median and interquartile range for continuous variables, and frequencies and proportions for categorical variables). We will also calculate descriptive statistics for outcomes at each study time point, and will explore differences in trajectories from baseline to 30 months follow-up between intervention and control groups using scatterplots and box-plots. Differences with 95% confidence intervals in continuous outcomes at 18 months (psychological community integration, self-esteem, social connectedness, hope, perceived housing quality, psychiatric symptoms, and sense of engulfment) between participants who received rent subsidies plus mentorship and participants who only received rent subsidies will be estimated using Analysis of Covariance (i.e., linear regression models), including an indicator of intervention group and the baseline value of the outcome. We will perform regression diagnostics and will repeat analyses using the non-parametric Wilcoxon

rank-sum test if there are extreme outliers or influential observations. Groups will be compared with respect to count outcomes at 18 months (physical community integration) using graphical tools and the non-parametric Wilcoxon rank-sum test. For binary outcomes at 18 months (sustained academic and vocational participation, and income above low income cut-off⁴), differences in proportions with 95% confidence intervals will be estimated and tested using the chi-square or Fisher's exact test. Given the small sample size of this pilot randomized trial, all results will be interpreted with caution and with the intention of generating data and hypotheses for conducting a larger trial.

All efforts will be made to reduce participants' attrition and drop-out. As mentioned previously, we believe our strong relationship with the outreach workers and community agencies will help minimize loss to follow-up (Slesnick et al., 2009). In addition, we have made it very clear in the participant information and consent form that participants in the rent subsidies plus mentorship arm may continue in the study (receiving only rent subsidies) if they are unable to continue in a mentor-mentee relationship.

5b. Qualitative Data

In keeping with the emergent, iterative nature of research using a qualitative design (Denzin & Lincoln, 2011; Eakin & Mykhalovskiy, 2003), data analysis and interpretation will begin immediately after the first qualitative data generation session (at baseline). The semi-structured individual interviews and focus groups will be audio recorded and transcribed verbatim. In order to conduct a more nuanced analysis of the data, the transcriptionist will be instructed to note short responses, uncooperative tones, and literal silence (Eakin & Mykhalovskiy; Kawabata & Gastaldo, 2015). Prior to each subsequent qualitative data generation session, members of the research team will conduct a preliminary data analysis, reading the interview transcripts multiple times, separating the data into coded segments, making analytic memos beside sections of the transcripts, identifying emerging themes (and comparing/contrasting these between respondents), and compiling new questions (Creswell, 2014; Denzin & Lincoln). Those participating in the individual interviews and the focus groups will be asked for their perspectives on the emerging interpretations at each visit and these perspectives will play a key role in helping shape the data analysis and help ensure the trustworthiness of the data (Creswell; Loiselle, Profetto-McGrath, Polit, & Tatano Beck, 2004). The web-based application Dedoose (SocioCultural Research Consultants, LLC, 2018) will be utilized to assist with sorting and coding the qualitative data.

⁴ Based on family and community size.

6. Ethical Considerations

There are important ethical considerations that must be considered with any type of research. This is especially true of RCTs conducted with marginalized populations (Solomon et al., 2009). Accordingly, we have endeavored to weave ethical considerations into all aspects of the study design (Solomon et al.), including our decision to utilize a CBPAR methodology and to modify the study design so that all of the participants will receive rent subsidies. Ethical approval for this study will be obtained from the Providence St. Joseph's and St. Michael's Healthcare Research Ethics Board (REB).

6a. Benefits and Risks to Participants

All of the study participants will likely find it beneficial to receive rent subsidies. Those randomized to the intervention group may also benefit from receiving regular interactions with a mentor. Participants selected for qualitative interviews might benefit from the opportunity to share their integration-related experiences with [name] on a regular basis. Additionally, participants may derive satisfaction from knowing that their contributions will help advance our understanding about how best to design interventions that assist formerly homeless young people to achieve meaningful social integration.

We believe theoretical justification exists for expecting that the proposed mentoring intervention is likely to produce effective outcomes; however, research ethics demands that we mitigate any potential risk to the research participants (Solomon et al., 2009). As previously mentioned, we will rely on the expertise of our community partners to screen and train the mentors. In addition, as highlighted previously, the outreach workers will work closely with the study participants and with our research team, and will alert our team if there are any concerns about a mentor-mentee relationship. These concerns will be relayed to our community partners so they can take appropriate action. The Providence St. Joseph's and St. Michael's Healthcare REB will be notified if a mentor-mentee relationship is terminated due to actions that violate the mentor-mentee code of conduct.

Participants will be assured that their participation or lack of participation in the study will not negatively impact their relationship with our community partners or their ability to access services at St. Michael's Hospital or support from other social services agencies (e.g., OW/ODSP).

6b. Privacy and Confidentiality

This mixed methods RCT will use multiple and varied data sources. This comprehensiveness is critical to the objectives of the study, yet may increase invasion of participant privacy. This privacy concern will be clearly communicated to potential participants, as will the measures for protecting security and confidentiality, prior to consent.

All of the data collected will be kept in strict confidence. While participants' names will appear on the consent forms, pseudonyms (created by the participants) will be used in place of their real names on all documents related to data generation, including the audio recordings and interview transcripts. A key that links each participant name with a pseudonym will be created and stored as a separate electronic file. All electronic data will be stored on secure servers at the Centre for Urban Health Solutions or the McMaster University School of Nursing, and only be accessible by select members of the research team.

The individual interviews and focus groups will be audio recorded using a password protected application on a password protected electronic device. The audio recordings from the individual interviews and focus groups will be deleted once the transcripts have been stored on the secure server and entered into Dedoose (encrypted and password-protected) (SocioCultural Research Consultants, LLC, 2018). Paper copies of the data (e.g., consent forms and standardized quantitative measures) will be stored in a locked filing cabinet at the Centre for Urban Health Solutions or at the McMaster University School of Nursing – areas only accessible to those with electronic and key access. All paper and electronic files will be retained for a period of up to five years from study closure.

The consent form indicates that limits to confidentiality apply if a participant discloses that they intended to hurt themselves or others, or if they inform a member of the research team that someone under the age of 16 years is suffering abuse and/or neglect.

7. Dissemination

In keeping with our CBPAR methodology, we are committed to disseminating evidence *with* our community partners to build community capacity and improve the lives of the young people participating in this study (Chenail et al., 2012; Wallerstein et al., 2018). Moreover, given our use of Critical Social Theory, we are obliged to not only present our findings, but to expose and explicate the relational processes (e.g., subjective experience of low socioeconomic position and low social class) that may be preventing formerly homeless young people from achieving meaningful social integration (Madison, 2012; Strega, 2005). With an emphasis on 'actionable' data (Chenail et al.), we anticipate disseminating our findings broadly to both academic and

community-based audiences in a variety of formats ranging from scientific journal papers to oral presentations.

7a. Documentary Film

Three study participants – one from each city – will be invited to participate in a documentary film. The primary purpose of the film is two-fold: 1) to highlight the impact of rent subsidies and mentorship on meaningful socioeconomic integration and 2) to advocate for enhanced economic and social supports for young people transitioning out of homelessness. We believe this form of dissemination is very much in keeping with our commitment to CBPAR methodology and Critical Social Theory scaffolding.

Participant recruitment and consent will take place as follows:

- [name] will reach out to three young people involved in qualitative interviews (all being conducted by [name]) that she believes would be good candidates for the film
- [name] will provide a high-level overview of the film and review the Participant Information and Consent: Documentary Film and St. Michael's Hospital Audio-Visual Consent for Non-Clinical Use forms with participants (will be e-mailed to participants prior to conversation)
- If participants are interested in learning more, [name] will connect them with film director/producer [name] in a three-way Zoom or telephone call ([name], [name], and the interested study participant – separate conversations with each potential film participant)
- During the three-way conversation, young people will be encouraged to ask questions about filming/screening
- After the three-way conversation, young people will be given 48 hours to consider participating (longer if needed) – after this period, [name] will reach out to them again
- Participants interested in taking part in the film will sign the Participant Information and Consent: Documentary Film and St. Michael's Hospital Audio-Visual Consent for Non-Clinical Use after reviewing them (again) with [name]
- After consent is received, [name] will inform [name], who will reach out to the participants and begin the process of filming

8. Limitations

This study has a number of limitations. First, the young people recruited for this pilot study will be a small sample of youth connected to urban-based social service providers in the province of Ontario. Thus, the findings may not be generalizable to formerly homeless young people living in other contexts and/or not connected to social service agencies. Second, the quantitative instruments are based on self-report and may

involve a degree of response bias. Finally, the quantitative measures we have chosen are what we believe to be surrogate markers of meaningful social integration. Future work will likely be needed to more accurately capture this complex concept.

9. Significance

This pilot RCT study will be the first to test the impact of economic and social supports on meaningful social integration for formerly homeless young people living in market rent housing. We believe the mixed methods design will illuminate important contextual factors that must be considered if the intervention is to be scaled up and replicated elsewhere. Importantly, the CBPAR framework will incorporate the perspectives of the community, including formerly homeless young people, who are in the best position to determine what might work best in the context of their lives.

References

Altena, A. M., Brilleslijper-Kater, S. N., & Wolf, J. R. (2010). Effective interventions for homeless youth: A systematic review. *American Journal of Preventive Medicine*, 38(6), 637-645. doi: 10.1016/j.amepre.2010.02.017.

Beck, A. T., Weissman, A., Lester, D., & Trexler, L. (1974). The measurement of pessimism: The hopelessness scale. *Journal of Consulting and Clinical Psychology*, 41(6), 639-660. doi: [10.1037/h0037562](https://doi.org/10.1037/h0037562).

Chenail, R. J., St. Goerge, S., Wulff, D., & Cooper, R. (2012). Action research: The methodologies. In P. L. Munhall (Ed.), *Nursing research: A qualitative perspective* (5th ed.) (pp. 455-470). Sudbury, MS: Jones & Bartlett.

Ciarolo, J. A., Edwards, D. W., Kiresuk, T. J., Newman, F. L., & Brown, T. R. (1981). *Colorado symptom index*. Washington, DC: National Institute of Mental Health.

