All of the study participants will be screened for eligibility (see criteria above) and recommended for the study by one of our community partners (Covenant House Toronto, Living Rock Ministries, and The RAFT). A member of the research team will call each recruited youth on the telephone and arrange to meet them at a location most convenient for the youth. Potential participants will be given a copy of the participant information and consent form to read. This document will also be reviewed verbally to ensure that those who have low literacy levels have been given the information required to give informed consent. During this process, the research team member will assess the capacity of the potential participant to provide free and informed consent. If it is unclear whether a youth is able to provide consent, the study co-investigator ([name]) will be contacted immediately. [name] will arrange for a qualified member of the research team to conduct a capacity assessment. If it is determined that a youth is not able to consent, they will be informed of this and they will be excluded from the study. The appropriate community partner will be notified as well.

3f. Allocation Procedure

[figure not shown]
If the participant meets the eligibility criteria, informed consent will be obtained, and the participant will be enrolled in the study. During this initial meeting, enrolled participants will participate in a baseline interview. There will be no unmasking of assignment prior to randomization. Following the baseline interview, participants at each of the three study sites (Toronto (n=12), Hamilton (n=6), and St. Catharine's (n=6)) will be randomized using block randomization to either the intervention (rent subsidies plus mentoring) or control (rent subsidies only) group. Randomization will be balanced by site based on random block sizes of two and four. The advantage of using block randomization is to uniformly distribute participants into treatment groups within each site (Efird, 2010). Because small block sizes may increase the risk of guessing the allocation procedure and subsequently introducing bias into the enrolment procedure, random block sizes will be used to avoid this potential selection bias (Suresh, 2011).

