A unique randomization schedule will be produced for each site using SAS (SAS Institute Inc., Cary, NC, USA), with the algorithm described in Efird (2010) and will be generated by a statistician based at St. Michael's Hospital. A research coordinator based at St. Michael's Hospital and not affiliated with the study will be the only person with access to the randomization schedule. The research coordinator will prepare sealed, opaque and sequentially numbered envelopes with the randomization results of participants. After assessing for eligibility and obtaining consent of each participant, research personnel responsible for enrolling participants will open the next randomization envelope from the sequentially ordered randomization envelope file to obtain the participant's randomized group assignment. Randomization envelopes for all sites will be held in a locked cabinet at Centre for Urban Health Solutions, St. Michael's Hospital. The research coordinator enrolling participants will record the participant's group allocation into the Participant Linking Log, record their Participant ID number onto the randomization envelope, and return all opened randomization envelopes to the independent research coordinator at St. Michael's Hospital. Subsequently, the independent St. Michael's research coordinator will complete the Master Randomization Assignment List with Participant ID numbers corresponding to each envelope number to check for consistency in participant allocation. Both the Participant Linking Log and Master Randomization Assignment List will be securely kept on St. Michael's Hospital servers.

Participants will be informed immediately if they have been allocated to the intervention or control group (Figure 1). In keeping with typical community-based RCTs with psychosocial interventions, 'blinding' in this study would not be pragmatic (e.g., social service providers and mentors will know if participants are in the 'treatment' group) after the baseline interviews and random assignments have been conducted (Solomon, Cavanaugh, & Draine, 2009).

Figure 1.

CONSORT (CONsolidation of the Standards Of Reporting Trials) Diagram of Ideal Flow of Participants Through the Study.

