***QT** = quantitative measures (all participants). These will consist of six standardized measures to assess: community integration, social connectedness, engulfment, hope, self-esteem, and psychiatric symptoms. As well, participants will complete two brief questionnaires pertaining to: 1) education (includes skills training), employment, and income; and 2) perceived housing quality. **QL** = qualitative measures (12 participants). These will consist of one-on-one semi-structured interviews with the same 12 participants (six from each arm). The interview questions will explore issues related to feasibility and acceptability, and provide context to the quantitative responses.

4. Data Generation

Undertaking a mixed methods study where data is truly ‘mixed’ at the level of collection (not just at analysis) is challenging because it requires a solid understanding of the data generation requirements of each research paradigm, and the interviews can take longer to conduct than those focusing on qualitative or quantitative

methods alone (Farquhar, Ewing, & Booth, 2011). To minimize respondent burden, we have given careful consideration to the type of quantitative instruments chosen (e.g., number and length of time to complete) and will ensure that appropriate components of the qualitative interviews are prioritized (e.g., follow-up on changes in instrument scores) at each data generation session (Farquhar et al.). Additionally, all of the mixed method interviews will be conducted by the co-investigator, [name], who has expertise in conducting mixed method interviews with young people who have experienced homelessness.

Quantitative data collection (questionnaires) took place via telephone rather than in-person following the publicly declared emergency due to the COVID-19 pandemic and will continue until the study end date of March 2022. Research staff have been noting participant responses on electronic copies of the questionnaire. The completed questionnaires have been securely kept on St. Michael's Hospital servers. In-person interviews have been conducted by [name] via virtual platforms, or telephone depending on participant preference. Conversations continue to be audio recorded using a password protected application on a password protected electronic device as described in the protocol.

4a. Study Outcomes

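### Can six interviewees per arm be invited at baseline when randomization comes after the baseline interview?

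*Combined protocol and SAP*

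**What the plan says.** Section 3f has every enrolled participant complete a baseline interview at the first meeting, and then: "Following the baseline interview, participants at each of the three study sites" are randomized, in blocks of two and four within site (12, 6 and 6 participants). The next paragraph of 3f describes the envelope step: "After assessing for eligibility and obtaining consent of each participant, research personnel responsible for enrolling participants will open the next randomization envelope". Participants are told their group at once. The closing paragraph of 3f, on why blinding is impractical, again puts baseline first: "after the baseline interviews and random assignments have been conducted".

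Section 4d covers the qualitative work: "At baseline, twelve participants (six from each arm of the study) will be invited to participate in" six semi-structured interviews, at the same six time points as the questionnaires, with the questionnaires always taken first. The key to Figure 1 repeats the quota: "one-on-one semi-structured interviews with the same 12 participants (six from each arm". Selection is purposive, with site, gender and ethno-racial spread as goals. Under section 4, "all of the mixed method interviews will be conducted by the co-investigator".

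On logistics, section 3e has the research team "arrange to meet them at a location most convenient for the youth", while in 3f "Randomization envelopes for all sites will be held in a locked cabinet at Centre for Urban Health Solutions".

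**The concern.** Inviting six people from each arm requires the arm to be known. If the baseline interview in 3f includes the qualitative part, the arm is not known when interviewees are chosen, and six per arm is left to chance. If the envelope is opened before the qualitative part, the quota can be met, but each first qualitative interview is with someone who already knows whether a mentor is coming. The text does not say which applies.

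The practical details add to the doubt. All envelopes sit in one cabinet, and whichever city holds it, at least 6 + 6 = 12 of the 24 participants are recruited elsewhere. The co-investigator runs the interviewees' sessions, questionnaires included, and so might have to attend baseline sessions before knowing who could be invited.

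Three things could be at stake: the balance of the qualitative subsample, the standing of the first interview as a true baseline, and, if scores were taken after allocation, the ANCOVA covariate. An uneven subsample could also let a difference between data collectors leak into the arm contrast.

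**Working it through.** **Order of events.** The plan gives no figure to reproduce, so the first check sets the sections side by side.

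1. The baseline interview in 3f is given to all 24 participants. What all 24 have in common is the questionnaire session. The 12-person component has its own name in 4d and in the figure key.
2. 4d puts questionnaires before the qualitative part at every visit.
3. 4d invites by arm, which presupposes that allocation has been revealed.
4. 3f reveals allocation immediately after randomization.

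Together these allow one workable order: questionnaires, envelope, invitation by arm, qualitative interview. It is an inference, because 4d also counts the questionnaires as part of the individual interview. On either reading, though, the baseline scores come before allocation. The envelope sentence in 3f names only eligibility and consent, but the paragraph before it and the closing paragraph of 3f both put baseline first.

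**If interviewees were nevertheless chosen before allocation.** Assume 12 per arm and 6, 3 and 3 interviewees from sites of 12, 6 and 6.

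*One random draw within each site, ignoring enrolment order.* The number from one arm is the sum of Hypergeometric(12, 6, 6) and two Hypergeometric(6, 3, 3) counts:
- exactly 6/6: 0.302
- 5/7 or closer: 0.757
- 4/8 or worse: 0.243

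*First-enrolled half of each site, using the plan's blocks.* Assume sizes two and four are equally likely.
- Large site, first six. A block of four straddles the sixth place if the sizes run 4, 4 (probability 1/4) or 2, 2, 4 (1/8), so 3/8 in all. The two places taken from that block fall in the same arm with probability 1/6 for each arm. Hence P(2) = P(4) = 3/8 × 1/6 = 0.0625 and P(3) = 0.875.
- Each small site, first three: the count is 1 or 2, each with probability 0.5. The two small sites together give 2, 3 or 4 with probabilities 0.25, 0.50 and 0.25.
- P(6/6) = 0.875 × 0.50 + 2 × 0.0625 × 0.25 = 0.469.
- P(5/7) = 2 × (0.875 × 0.25 + 0.0625 × 0.50) = 0.500.
- P(4/8) = 2 × 0.0625 × 0.25 = 0.031. Nothing worse is possible.

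The 24% chance of a 4/8 split or worse therefore belongs to a draw that ignores the plan's own blocks. With them it is about 3%. Because each allocation is disclosed at once, later invitations could also be adjusted.

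**Leak into the arm contrast.** The documents give no data-collector effect. Assume 0.2 to 0.5 SD.
- 5/7 split: shift = 2/12 × (0.2 to 0.5) = 0.03 to 0.08 SD.
- 4/8 split: shift = 4/12 × (0.2 to 0.5) = 0.07 to 0.17 SD.
- ANCOVA standard error, √(2/12) × √(1 − ρ²), with assumed baseline correlation ρ of 0.3 to 0.7: 0.39 to 0.29 SD.

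The shift is below the standard error throughout, and it is zero at 6/6.

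**The case for a change.** The best case for the concern is that the gap is real on the page. No sentence places the envelope relative to the first qualitative interview, and the workable order has to be pieced together. Objective 4 uses the qualitative material to interpret the quantitative results, and section 4 has the interviews follow up changes in scores. Whether the first account came before knowledge of allocation therefore affects how change within a person is read. In a pilot meant to inform a larger trial, one sentence giving the order would cost almost nothing.

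Part of this stands. The visible text is silent, and on the workable order the first qualitative interview is not a pre-allocation account. But the place to show the order is the flow diagram, whose key carries the labels for the quantitative and qualitative measures; it is not reproduced, so it cannot be counted as missing. No objective calls for a pre-allocation qualitative account. The interviews are there for context, feasibility and acceptability, and six per arm is an invitation target within a purposive sample.

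The logistical points carry less weight. The cabinet sentence describes storage: enrolling staff open the next envelope, mark it and return it, and nothing requires the participant to be beside the cabinet. Nor does 4d say that the invitation and first interview must fall on the day of enrolment, although it does tie the interview to the baseline time point.

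**Conclusion.** No change to the plan follows. This is a gap in wording that the study team fills sensibly by following the sections together: questionnaires, envelope, invitation by arm, qualitative interview. On that order six per arm is attainable, and the baseline scores used in the ANCOVA precede allocation. The one consequence is that the first qualitative interview is held with allocation known, which ordinary reporting of the qualitative work can make clear.

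If interviewees were instead chosen before allocation, the expected imbalance is small: 5/7 or closer in about 97% of cases, assuming first-enrolled interviewees, a 6/3/3 spread across sites and equally likely block sizes. Any effect on the arm contrast would be indirect, rests on an assumed data-collector difference, and stays below the standard error. A sensitivity analysis without baseline adjustment would gain nothing: no section puts a baseline score after allocation, and the 95% half-width would be about 0.85 SD (√(2/12) × t on 22 df) against 0.61 to 0.81 SD with ANCOVA at the assumed correlations.
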